5.6 End of Study Evaluation

All patients will be followed 14-30 days after the last dose of BBI608. If a patient is removed from the study due to drug-related adverse events, the patient will be followed to evaluate any drug-related AEs that occurred either during the study or within 30 days of the last BBI608 dose. The patient will be followed until resolution of the AE or for 30 days, whichever is longer. In the presence of toxic effects, follow-up visits will be required every four weeks until all study related toxicities have resolved to baseline (or < CTCAE Grade 1), have stabilized, or are deemed irreversible.

The following assessments will be made during the End of Study visit:

- Physical examination including a neurological examination
- ECOG performance status score
- Vital signs (weight, temperature, blood pressure, respiration and pulse)

- Serum pregnancy test (if applicable)
- Hematology (see Section 6.3)
- Biochemistry (see Section 6.3)
- Urinalysis (see Section 6.3)
- 12-lead ECG
- Tumor marker, if applicable
- Tumor measurement and staging if applicable
- Assess adverse events
- Record concomitant medications including any changes in doses of corticosteroids

After BBI608 administration is discontinued and after the EOS study visit has been completed, patients will be followed for important information and the occurrence of specified clinical endpoints: PFS and OS. There are no further visits required specifically for this study once the EOS visit has taken place.

The clinical parameters and endpoints for follow-up are specified below. The intent is that the follow-up and collection of this information is accomplished through review of the local medical record system by site study staff and/or study CRAs-Monitors. Contact with the primary oncologist and/or primary care physician for a given patient may also be required.

Clinical Parameters for Post-Protocol Therapy Follow-Up

Endpoint	Description	Follow-Up Frequency
Subsequent Therapy	Names and dates of anti-cancer treatment administered after BBI608 discontinuation. "Clinical Trial" can also be used if agent name is not publically available	Evidence for clinical endpoints will be assessed monthly for the first 3 months after discontinuing BBI608 Then,
Objective Disease Progression	Date criteria for RANO categorization of "PD" are met (if not already met during on-study or EOS objective assessments)*	Every 3 months up to 1 year after discontinuing BBI608 Then,
Survival	Date of death due to any cause	Every 6 months thereafter**

*Passive follow-up only of radiologic imaging obtained subsequent to all on-study MRI scans and clinic visit notes detailing neurologic state and change in corticosteroid use.

**Alternative schedules of post-protocol therapy follow-up by study site may be discussed with the Sponsor.

5.7 Discontinuation from Study

Patients will be removed from the study at any time if they meet any of the following criteria:

- Documented radiologic or clinical progression of disease

- Noncompliance with any part of the study, as evaluated by the Principal Investigator and Medical Monitor
- Withdrawal of consent
- Investigator decision
- Lost to Follow-up
- Death
- Clinically unacceptable toxicities despite optimal treatment or dose reduction
- Pregnancy

*RANO criteria serve to categorize clinical radiologic images. Given a unique mechanism of action targeting cancer stem cells, BBI608 therapy may be continued in a patient who is clinically well, but who meets criteria for “Progressed Disease” per RANO criteria. Continuation of BBI608 protocol therapy in this context is allowed provided no further standard, approved treatment options exist; and provided the investigator assess that the potential benefit to the patient outweighs the potential risk and in the absence of intolerable toxicities, performance status decline, worsening of disease related symptoms, radiological findings that would warrant acute intervention and no ongoing severe toxicities that may be related to BBI608. The patient will also get repeat tumor assessments after 4-6 weeks. Treatment with BBI608 (with or without TMZ) will continue until unacceptable toxicity, further disease progression (clinical or radiological), or another discontinuation criterion is met.

5.7.1 Dates Associated with Discontinuation from Study

The following clarifies important dates at the end of study treatment:

Date of Last Dose: The date that the last dose of BBI608 is taken. *The Date of Last Dose* does not necessarily need to be the *Date Off Active Study*.

Date Off Active Study: The date when both the patient and the investigator/study team understand the patient to be off of active protocol treatment. In most cases, this will be the same as the *Date of Last Dose*; however, it does not need to be the case. In addition, the *Date Off Active Study* may not coincide with a formal study visit.

End of Study Visit: A formal study visit held 30 days after the *Date of Last Dose*.

6 STUDY PROCEDURES

6.1 Medical History

Medical history will include, but is not limited to, the following:

- Demography: date of birth, sex, ethnic origin, height, weight, smoking history
- Clinically significant prior diagnoses, surgeries, and current medications
- Prior cancer history, current cancer diagnosis, tumor stage at time of diagnosis, previous surgical therapy, previous chemotherapy, including dates and duration of

treatment, previous radiation therapy, including anatomic site, dose and date of treatment, O-6-methylguanine-DNA methyltransferase (MGMT) methylation status

Prior records, radiology reports, radiology imaging, or procedure notes may be required in order to verify components of study patient history.

6.2 Physical Examination

Complete physical examination including height, weight, blood pressure, heart rate, respiratory rate, temperature (oral, axillary or tympanic) and ECOG performance status score.

6.3 Clinical Laboratory Tests

Safety laboratory determinations will include hematology, blood chemistry, and urinalyses. All laboratory tests required during the study must be obtained at a primary laboratory designated by the Principal Investigator.

- Hematology: CBC including hemoglobin, white blood cell count with 5-part differential, platelets
- Biochemistry: electrolytes (sodium, potassium, and chloride), CO₂, calcium, phosphorus, magnesium, total protein, albumin, glucose, and serum creatinine, blood urea nitrogen (BUN), AST, ALT, lactate dehydrogenase (LDH), alkaline phosphatase, total and direct bilirubin, and uric acid
- Routine urinalysis: dipstick including protein, specific gravity, glucose and blood
- Serum pregnancy test for female patients of childbearing potential

MGMT methylation status: MGMT promoter methylation status will be assessed on archival tumor tissue submitted at enrollment, as well as tumor tissue obtained during the course of the study (i.e. specimen from surgical resection)

6.4 Pharmacokinetic Assessments

Patients enrolled into Arm A of the study will have blood and tumor tissue samples obtained at the time of surgical resection to evaluate the levels of BBI608 in plasma and tumor tissue. A single blood sample will be obtained as close to the time of tumor resection as possible. The time of BBI608 administration on the day of surgery and the collection times of blood sample will be recorded. Details on the collection, storage and shipping of these samples are described in the Laboratory Manual.

Additionally, blood samples will be collected from all patients in the Phase Ib/DLT assessment cohorts to assess the pharmacokinetics (PK) of BBI608 and TMZ. Collection, storage, and shipping of PK samples will be performed as described in the Laboratory Manual at time points outlined below:

Day	Procedure	Sample No.	Desired Time
1	Draw blood sample	PK-01	0 hr (pre-dose)
	First daily BBI608 dose		0
	Draw blood sample	PK-02	0.5 hr
	Draw blood sample	PK-03	1 hr
	Draw blood sample	PK-04	2 hr
	Temozolomide Administration ^a		3 hr
	Draw blood sample	PK-05	3 hr
	Draw blood sample	PK-06	4 hr
	Draw blood sample	PK-07	5 hr
	Draw blood sample	PK-08	7 hr
	Draw blood sample	PK-09	10 hr
	Draw blood sample	PK-10	12 hr
Day	Procedure	Sample No.	Desired Time
5	Draw blood sample	PK-11	0 hr (pre-dose)
	First daily BBI608 dose		0
	Draw blood sample	PK-12	0.5 hr
	Draw blood sample	PK-13	1 hr
	Draw blood sample	PK-14	2 hr
	Temozolomide Administration ^a		3 hr
	Draw blood sample	PK-15	3 hr
	Draw blood sample	PK-16	4 hr
	Draw blood sample	PK-17	5 hr
	Draw blood sample	PK-18	7 hr
	Draw blood sample	PK-19	10 hr
	Draw blood sample	PK-20	12 hr

^aTemozolomide will be administered 3 hours after BBI608 during PK assessments

6.5 Pharmacodynamic Assessments

Pre-clinical and clinical studies conducted by BBI have identified several biomarkers in tumor tissues whose levels either increase or decrease upon exposure to BBI608. Archival tumor samples will be collected from patients in both study arms. On-study tumor samples following 1 week of treatment with BBI608 monotherapy prior to surgical resection will be collected ONLY from patients enrolled into Arm A, as described below. The goal of the proposed biomarker study is to examine the response of biomarkers in patients treated with BBI608 monotherapy. Subject tumor samples will be processed for determination of pharmacodynamic markers in malignant tissue by histopathology and cancer stem cell (CSC) assays.

6.6 Archival and On-Study Tumor Tissue Collection

Archival formalin fixed paraffin-embedded (FFPE) tissue samples from a previous resection or biopsy of the patient's glioblastoma should be collected from all patients enrolled in the clinical trial.

For patients enrolled into Arm A, the archival tumor tissue will serve as a *baseline* sample prior to starting treatment with BBI608. An *on-treatment* tumor sample will be collected during the surgical tumor resection, following completion of the 1-week BBI608 monotherapy treatment.

Tumor samples that are obtained at the time of surgical resection and are labeled with study protocol identification number and patient identification number will be sent to a regulatory authority-approved tumor bank affiliated with the study site, or to the study site pathology department if the site does not have a regulatory authority-approved tumor bank. Appropriately processed tumor specimens would be then forwarded to the Sponsor or Sponsor CRO for analysis. Processing of all tumor tissue will include creation of both fresh frozen samples for PK analysis as well as blocks of formalin fixed paraffin-embedded (FFPE) samples for PD analysis.

Collection, storage, and shipping of tissue samples will be performed as described in the accompanying Laboratory Manual.

Other investigations on tumor samples may be performed as determined by the study investigators and/or study sponsors. If the patient grants permission, tumor samples may be stored for additional future studies.

Please see the Laboratory Manual for this study for more information regarding collection, processing, storage and shipment of tumor sample tissue.

7 TREATMENT

7.1 BBI608

BBI608 capsules will be supplied to the pharmacy at the clinical sites. Study drug will be labeled as an investigational agent, limited by federal law. The pharmacist will dispense an appropriate number of each strength capsule to the Principal Investigator for in-clinic dosing. The appropriate quantity of capsules will be dispensed to the patient for each cycle (see Section 5.4 and Appendices A and B).

BBI608 is supplied as 80 mg capsules and should be stored at room temperature (15-25 degrees Celsius). These instructions must appear on the label for the container in which capsules are delivered to the patient.

7.1.1 Investigational Product Accountability

BBI will provide all study drug required for completion of this study. The recipient will acknowledge receipt of the drug indicating shipment content and condition. Damaged supplies will be replaced. Until dispensed to the patients, the 80 mg capsules will be stored in a temperature controlled, secure locked area, accessible to authorized personnel only, at room temperature (15-25 degrees Celsius).

Accurate records of all study drug dispensed from and returned to the study site are to be maintained. The study site must supply a copy of their drug destruction policy to BBI before authorization for destruction will be granted. Product accountability will be monitored throughout the study. Upon completion or termination of the study, and after inventory by a BBI monitor or designated representative, all unopened drug is to be returned to BBI, or designee, in the original containers.

7.1.2 BBI608 Administration

BBI608 will be administered continuously by mouth twice daily, with doses approximately 12 hours apart. BBI608 should be administered approximately one hour prior to or two hours after meals, and the first dose should be given in the morning.

The dose of BBI608 to be administered depends on the dose level to which the patient is enrolled. See Section 4.1 for details.

7.1.3 Temozolomide (TMZ) Administration

Detailed instructions for the preparation, premedication, and administration of TMZ are provided in the Product Labels approved by Health Canada or US FDA. Temozolomide is a standard of care medication and will not be provided by the Sponsor.

TMZ 150 mg/m² will be administered orally to patients enrolled into arms A and B, beginning on Day1 of Cycle 1 of combination treatment. TMZ will be administered on days 1 through 5 of each 28-day combination therapy cycle. In case of toxicity, dose adjustment is permitted. If TMZ is tolerated at the 150 mg/m² once daily dose, dosage may be increased to 200 mg/m² once daily dose after the first cycle.

A 3 hour interval between the first daily dose of BBI608 and the initiation of TMZ is required on PK days (i.e. C1D1 and C1D5) during Cycle 1 only, in order to standardize PK interpretation. On all other days, the first daily administration of BBI608 should precede the administration of TMZ by 0-4 hours.

7.2 Dose Modifications

7.2.1 BBI608

For any suspected BBI608-related grade 3 or intolerable grade 2 adverse events that persist despite optimized medical management (see Table 1), a dose holiday of 0.5-3 days followed by dose modification as outlined in the table below is recommended. Investigators should

discuss dose modifications with the Medical Monitor for the Sponsor. Patients should up-titrate dose with the goal of achieving full dose as tolerated.

Suggested Management for AEs Associated with BBI608 Administration

Suspected BBI608 -Related Adverse Event	Investigator Action
Grade 1 or tolerable Grade 2 Symptoms	
 •Patient should remain at current dose. Attempt pharmacologic measures to minimize symptoms (see Table 1 below).
Intolerable Grade 2 Symptoms	
 •If intolerable symptoms persist despite optimized medical management, dose reduction and sufficient oral hydration are recommended. A dose interruption of ½ to 3 days prior to reduction can also be considered. •Dosing should be reduced to the next Modification Level on the dose modification table. Pharmacologic symptom support and/or prophylaxis should be maintained (see Table 1). •After a dose reduction, AM and PM doses may be increased in 80 mg increments every 3-7 days as tolerated.*, **
Grade 3 or 4 Symptoms	
 •A dose interruption of ½ to 3 days is recommended until symptoms are reduced to ≤ grade 2. •Dosing should be reduced to the next Modification Level on the dose modification table. Pharmacologic symptom support and/or prophylaxis should be maintained (see Table 1). •After a dose reduction, AM and PM doses may be increased in 80 mg increments every 3-7 days as tolerated.*, **

* If, during the course of re-escalation, a dosing regimen is not tolerated despite optimized medical management, dosing should return to the highest previously tolerated dosing regimen.
 
** Asymmetry between AM and PM dose is allowed during re-escalation (e.g. 320 mg AM/240 mg PM).
	

BBI608 Dose Modification Table:

Dose Level	Dose
Full dose	480 mg twice daily (q12h)
Modification Level-1	240 mg twice daily (q12h), up titrate as tolerated**
Modification Level-2	80 mg twice daily (q12h), up-titrate as tolerated**
Modification Level-3	80 mg once daily*, up-titrate as tolerated**

* If 80 mg once daily is not tolerated, a dose interruption of 1-3 days followed by re-challenge at 80 mg once daily is recommended.
 
** Morning and evening doses can be increased in 80 mg increments every 3-7 days or slower as tolerated, up to 480 mg two times daily.
	

Table 1: Supportive Pharmacology for Adverse Events Associated with BBI608 Administration

Diarrhea & Abdominal Cramping	Nausea, Vomiting, or Anorexia

Dicyclomine (e.g., Bentyl): Recommended when the predominant issue is cramping or abdominal pain
	
1st line: 5HT3-inhibitors (Ondansetron, Palonosetron, Granisetron)

Diphenoxylate/atropine (Lomotil) Loperamide (Imodium)
 
These agents may be particularly useful in combination
	
2nd line: Dexamethasone (Decadron), ideally in combination with a 5HT3-inhibitor. Short term use can be very effective

Systemic opioids (e.g. Dilaudid, Codeine): have been found effective in reducing abdominal pain and watery diarrhea
	
Other agents: anti-histamines, benzodiazepines, proton pump inhibitors/H2 antagonists, dopamine antagonists, and cannabinoids

Hyoscine (Buscopan, Scopolamine, Levsin): Anti-spasmodic agents helpful for abdominal cramping
	

Budesonide (Entocort EC): Topical Corticosteroid with limited systemic absorption; 9mg PO once daily for 8 to 12 weeks
	

It is recommended adding Budesonide prophylaxis to improve GI tolerability of BBI608.

Start prophylactic Budesonide 9mg QD PO, 24 hours prior to the first dose of BBI608 on Cycle 1, Day 1. Take Budesonide at least 2 hours apart from BBI608 and TMZ, either before or after taking BBI608 and TMZ. Continue to take Budesonide for 8 to 12 weeks.

7.2.2 Temozolomide

Serious toxicities attributable to TMZ include neutropenia, thrombocytopenia, lymphopenia, *pneumocystis* pneumonia, and hepatotoxicity. Common adverse side-effects of TMZ include nausea and vomiting. Please see the Package Insert for full prescribing and toxicity information.

Cycle 1: Dosage in Cycle 1 (maintenance) is 150 mg/m² once daily for 5 days followed by 23 days without treatment. Cycles 2-6:

At the start of Cycle 2, the dose can be escalated to 200 mg/m², if the CTC non-hematologic toxicity for Cycle 1 is Grade less than or equal to 2 (except for alopecia, nausea, and vomiting), absolute neutrophil count (ANC) is greater than or equal to 1.5 x 10⁹ /L, and the platelet count is greater than or equal to 100 x 10⁹ /L.

The dose remains at 200 mg/m² per day for the first 5 days of each subsequent cycle except if toxicity occurs. If the dose was not escalated at Cycle 2, escalation should not be done in subsequent cycles.

Dose Reduction or Discontinuation:

Dose reductions should be applied according to Tables 2 and 3.

During treatment, a complete blood count should be obtained on Day 22 (21 days after the first dose of TEMODAR) or within 48 hours of that day, and weekly until the ANC is above 1.5 x 10⁹ /L (1500/μL) and the platelet count exceeds 100 x 10⁹ /L (100,000/μL).

The next cycle of TEMODAR should not be started until the ANC and platelet count exceed these levels. Dose reductions during the next cycle should be based on the lowest blood counts and worst non-hematologic toxicity during the previous cycle.

Dose discontinuations should be applied according to Tables 2 and 3.

Table 2: Temozolomide Dose Levels for Maintenance Treatment

Dose Level	Dose (mg/m ² /day)	Remarks
-1	100	Reduction to prior toxicity
0	150	Dose during Cycle 1
1	200	Dose during Cycles 2-6 in absence of toxicity

Table 3: Temozolomide Dose Reduction or Discontinuation During Maintenance Treatment

[figure not shown]
Toxicity	Reduce TMZ by 1 Dose Level*	Discontinue TMZ
Absolute Neutrophil Count	Less than 1.0 x 10	See footnote†
Platelet Count	Less than 50 x 10	See footnote†
C Nonhematological Toxicity (except for alopecia, nausea, vomiting)	CTC Grade 3	CTC Grade 4

*TMZ dose levels are listed in Table 2.

† TMZ is to be discontinued if dose reduction to less than 100 mg/m² is required or if the same Grade 3 nonhematological toxicity (except for alopecia, nausea, vomiting) recurs after dose reduction. TMZ=temozolomide; CTC=Common Toxicity Criteria.

Dose modifications for toxicities attributed to TMZ should be performed according to institutional standards or as per Product Labels approved by Health Canada or US FDA (see Package Insert,). Dose Modification instructions taken from the US Package Insert appear below in Figure 1 for reference:

Figure 1 Dose Modification Instructions for Temozolomide

If a toxicity is thought by the Investigator to be related to both BBI608 and TMZ combination regimen, then the dose modification rules for both BBI608 and temozolomide should be followed.

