5.4.3.5 Cycle 1 and Cycle 2 Day 22 (during Phase Ib)

The patient will have the following assessments:

- Hematology (see Section 6.3)
- Biochemistry (see Section 6.3)
- Urinalysis (see Section 6.3)

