5.4.3.6 Cycle 2 and Beyond

Day 1

- Physical examination including a neurologic examination
- ECOG performance status score

- Vital signs (weight, temperature, blood pressure, respiration and pulse)
- Serum pregnancy test (if applicable)
- Hematology (see Section 6.3)
- Biochemistry (see Section 6.3)
- Urinalysis (see Section 6.3)
- Assess adverse events (AE)
- Record concomitant medication including any changes in doses of corticosteroids
- Dispense BBI608 (28 day supply plus 3 days), please see the Pharmacy Manual for further information
- Dispense TMZ

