10.6 Safety Analysis

Safety will be assessed by physical examination, and laboratory assessments. Weekly laboratory testing is required during the first 2 cycles of Phase Ib. Adverse events will be graded according to the NCI CTCAE, version 4.0. The incidence of DLTs will be evaluated for in all patients enrolled into a safety cohort for each of the study arms. The incidence of adverse events will be evaluated for all patients. All patients will be followed for adverse events for at least 30 days after the last dose of BBI608, or until recovery from all study drug related adverse events.

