APPENDIX A: SCHEDULE OF ASSESSMENTS (ARM A)

Procedure	Baseline	BBI608 Monotherapy Run-in		Combination Cycle				Additional Cycles	End of Study Visit
		Day 1	Day 8 (Surgery)	Day 5	Day 8	Day 15	Day 22		
Timing (+/- 3 days, unless otherwise noted)	Up to 10 days prior to first dose							Day 1	30 days from last BBI608 dose
Written informed consent ¹	X								
Medical history	X								
Physical examination	X							X	X
Vital signs	X	X	X	X				X	X
ECOG performance status score	X		X	X				X	X
Serum pregnancy test	X							X	X
Hematology ²	X		X	X	X			X	X
Biochemistry ²	X		X	X	X			X	X
Urinalysis ²	X		X	X	X			X	X
12-Lead electrocardiogram	X								X
Tumor Resection ³			X						
Pharmacokinetics ⁴									
Tumor Assessment ^{5,6,7,8}	X ⁵		X ⁸					every 8 weeks from Cycle 1 Day 1	X
Concomitant medications	X	X	X	X				X	X
Adverse events	X	X	X	X				X	X ⁹
Dispense TMZ ¹⁰								X	
Dispense BBI608		X						X	

1. Written informed consent may be obtained up to 1 month prior to first dose of BBI608
 2. See Section 6.3 These test must be obtained at Day 1,8,15 and 22 of Cycle 1 and Cycle 2

-
3. Resected tumor tissue will be collected for pharmacodynamics and pharmacokinetic evaluations (see Sections 6.4, 6.5 and 6.6.). Blood samples will be collected at the time of surgery for pharmacokinetic evaluation. Archival FFPE tumor tissue will be collected for all patients.
 4. Pharmacokinetics on day 1 and 5 of cycle 1 will only be performed on patients in the Phase Ib/DLT assessment cohorts
 5. Including tumor measurements, following RANO criteria
 6. At the end of cycle 2 (+/-7 days) of combination therapy and every 8 weeks thereafter (+/-7 days), assessments should be made utilizing the same imaging method as baseline and preferably the same imaging machine.
 7. MRI scan performed within 28 days of the first scheduled dose of BBI608 can be used for baseline assessment
 8. MRI scan will be performed within 48-72 hours of surgery in Arm A patients as a baseline scan for the purposes of tumor response assessment.
 9. Patients will be followed until resolution of any drug-related AE or SAE occurring during the study or within 30 days of last BBI608 administration.
 10. TMZ will be administered from day 1 to 5 of every 28 day cycle.

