APPENDIX B: SCHEDULE OF ASSESSMENTS (ARM B)

Procedure	Baseline Up to 10 days prior to first dose	Combination Cycle				Additional Cycles	End of Study Visit 30 days from last BBI608 dose	
		Day 1	Day 5	Day 8	Day 15			Day 22
Timing (+/- 2 days, unless otherwise noted)						Day 1		
Written informed consent ¹	X							
Medical history	X							
Physical examination	X	X ⁹				X	X	
Vital signs	X	X		X		X	X	
ECOG performance status score	X	X ⁹		X		X	X	
Serum pregnancy test	X					X	X	
Hematology ²	X	X ⁹		X	x	X	X	
Biochemistry ²	X	X ⁹		X	x	X	X	
Urinalysis ²	X	X ⁹		X	x	X	X	
12-Lead electrocardiogram	X	X					X	
Pharmacokinetics ³		X						
Tumor Assessment ^{4,5,6}	X ³		every 8 weeks from Cycle 1 Day 1					X
Concomitant medications	X	X		X		X	X	
Adverse events	X	X		X		X	X ⁷	
Dispense TMZ ⁸		X				X		
Dispense BBI608		X				X		

1. Written informed consent may be obtained up to 1 month prior to first dose of BBI608

2. See Section 6.3 These test must be obtained at Day 1, 8, 15 and 22 of Cycle 1 and Cycle 2

3. Pharmacokinetics on day 1 and 5 of cycle 1 will only be performed on patients in the Phase Ib/DLT assessment cohorts

4. Including tumor measurements, following RANO criteria

5. At the end of cycle 2 (+/7 days) of combination therapy and every 8 weeks thereafter (+/-7 days), assessments should be made utilizing the same imaging method as baseline and preferably the same imaging machine.

6. MRI scan performed within 28 days of the first scheduled dose of BBI608 can be used for baseline assessment.

7. Patients will be followed until resolution of any drug-related AE or SAE occurring during the study or within 30 days of last BBI608 administration.

8. TMZ will be administered from day 1 to 5 of every 28 day cycle.

9. Performed only if the baseline assessments are done prior to 10 days of Cycle 1 Day 1.

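### The temozolomide (TMZ) dose rule relies on a Day 22 blood count in every cycle, but the visit lists stop scheduling it after Cycle 2, and two sections limit it to Phase Ib

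*Protocol*

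**What the plan says.** Protocol Section 7.2.2 sets the monitoring rule for TMZ: "During treatment, a complete blood count should be obtained on Day 22 (21 days after the first dose of TEMODAR", with a 48-hour allowance and weekly repeats until ANC is above 1.5 and platelets are above 100 (x10^9/L). TMZ may not restart until both levels are exceeded. The dose itself looks back over the whole cycle: "Dose reductions during the next cycle should be based on the lowest blood counts and worst non-hematologic toxicity during the previous cycle". Table 3 lowers TMZ by one level if ANC was below 1.0 or platelets were below 50.

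The visit texts say the following.

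- Appendix A, footnote 2, on hematology, biochemistry and urinalysis: "These test must be obtained at Day 1,8,15 and 22 of Cycle 1 and Cycle 2". Appendix B, footnote 2, is the same in substance: "These test must be obtained at Day 1, 8, 15 and 22 of Cycle 1 and Cycle 2". Neither sets a phase limit, and neither goes past Cycle 2.
- The study-visit section heads the Day 22 visit "5.4.3.5 Cycle 1 and Cycle 2 Day 22 (during Phase Ib".
- Section 10.6 agrees with that heading: "Weekly laboratory testing is required during the first 2 cycles of Phase Ib".
- Section "5.4.3.6 Cycle 2 and Beyond" lists hematology on Day 1 and no other day.

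SAP Section 8.2.4.2 builds the ANC and platelet shift tables on the worst grade after baseline.

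**The concern.** The dose rule needs a mid-cycle count, yet the sections that tell a site when to draw blood do not carry it past Cycle 2. They also disagree on whether Phase II patients have it at all. Protocol Section 5.1 sends sites to Appendices A and B for the schedule, so an instruction found only under dose modification is easy to overlook.

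Two things are at stake. For the patient, a count low enough to require a TMZ reduction could come and go unseen, and TMZ would be repeated at the same dose, up to 200 mg/m², alongside daily BBI608. For the analysis, the worst hematological grade would depend on which section a site followed. Section 7.2.2 itself names neutropenia and thrombocytopenia among the serious toxicities of TMZ.

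**Working it through.** There is no stated figure to reproduce. The check sets the texts side by side and counts days.

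**Step 1. Where a Day 22 count is called for.**

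| Protocol text | Cycles 1-2, Phase Ib | Cycles 1-2, Phase II | Cycle 3 onward |
|---|---|---|---|
| Section 7.2.2 | yes | yes | yes |
| Appendices A and B, footnote 2 | yes | yes | no |
| Sections 5.4.3.5 and 10.6 | yes | no | no |
| Section 5.4.3.6 (from Cycle 2) | Day 1 only | Day 1 only | Day 1 only |

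All the texts that cover Cycle 1 agree only for Phase Ib. This reading rests on footnote 2 and Sections 5.4.3.3 to 5.4.3.6, not on the cell layout of the appendix grids.

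**Step 2. Can a scheduled visit stand in for Day 22?** The first TMZ dose is on Day 1, and 1 + 21 = Day 22, so Section 7.2.2 is consistent within itself. Its window is 22 ± 2, or Days 20 to 24. From Cycle 3 the next scheduled count is Day 1 of the following cycle, which is 28 + 1 = Day 29.

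- With the ±2 days of Section 5.1: Days 27 to 31.
- With the ±3 days in Appendix A: Days 26 to 32.

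Neither range overlaps Days 20 to 24.

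**Step 3. Which low counts would go unseen?** Suppose a site draws only the Day 1 count from Cycle 3.

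- ANC still at or below 1.5, or platelets still at or below 100, on Day 29: TMZ is held under the restart rule, so the problem is seen.
- ANC was below 1.0 and is above 1.5 by Day 29, or platelets were below 50 and are above 100 by Day 29, with the other count also clear: TMZ restarts. The record shows no Table 3 trigger, and the dose is not reduced.

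Only the second case is lost. It needs full recovery to the restart level within about 29 - 22 = 7 days of the Day 22 draw.

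**Step 4. Size of the schedule gap per patient.** For a patient who starts n TMZ cycles (n at least 2), Section 7.2.2 asks for n Day 22 counts.

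- Footnote 2 schedules 2, leaving n - 2 unscheduled.
- Sections 5.4.3.5 and 10.6 also leave n - 2 for a Phase Ib patient, but all n for a Phase II patient.

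With n = 6, the last cycle that Table 2 of Section 7.2.2 mentions, this is 6 - 2 = 4 of 6 (67%) under footnote 2, and 6 of 6 for a Phase II patient under the narrower texts. Section 4.1 allows 24 further patients per arm after the six-patient safety cohort. If a second safety cohort is needed and the arm stays at 30, that falls to 30 - 12 = 18.

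**Step 5. What is untouched?** In Phase Ib Cycle 1, footnote 2 and Sections 5.4.3.5, 7.2.2 and 10.6 all provide Day 22 hematology. The DLT window is the first 28 days of combination treatment, so the DLT decision has its counts. PFS-6 rests on progression and death and uses no blood count.

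**The case against.** The best defence is that the test is not missing. Section 7.2.2 is current protocol text and asks for the count without limit. The visit lists do not say that nothing else may be drawn, and Section 5.1 allows unscheduled assessments. A site that follows the whole protocol draws the count. This stands, and it makes the fault a conflict between sections rather than an absent safeguard. It does not remove the conflict, because Section 5.1 permits extra assessments without requiring them.

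Two further safeguards also stand. The Day 1 restart rule catches every partial recovery. SAP Section 8.2.4.2 includes unscheduled laboratory results in the shift tables, so a count drawn because of Section 7.2.2 is analysed even if no visit lists it. In Cycles 1 and 2 the Day 15 count, scheduled in both phases, could catch some low values.

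A reader might infer more than the documents support, in three ways.

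- *A number of missed reductions per arm.* The documents do not say how often a Day 22 count meets Table 3 and recovers by Day 29. An arm-level total would also need time on treatment, the number of safety cohorts, and Arm A's lag before combination therapy: 5 to 9 days of run-in plus 15 to 28 days after surgery, or 20 to 37 days.
- *Harm to the primary results.* Step 5 above rules this out for the Phase Ib DLT endpoint and for PFS-6.
- *A second defect in the later sentence of Section 7.2.2*, "Dose modifications for toxicities attributed to TMZ should be performed according to institutional standards or as per Product Labels". It is not ranked against Tables 2 and 3, but it introduces the label instructions in Figure 1, which could not be read for this point. Confining it to the toxicities that Table 3 excludes would leave lymphopenia, which Section 7.2.2 lists as serious, without a rule. No change to that sentence is proposed.

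**Conclusion.** The inconsistency is real and worth correcting. From Cycle 3, no visit text schedules the Day 22 count that Section 7.2.2 asks for. For Phase II patients, Sections 5.4.3.5 and 10.6 do not schedule it in any cycle, while footnote 2 does so in Cycles 1 and 2.

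The consequence is narrow. It assumes a site that works from the visit lists and a patient whose count falls below a Table 3 threshold and then recovers above the restart level by the next Day 1. In that case the TMZ reduction is not applied and the worst-grade tables miss the event. If every site follows Section 7.2.2, nothing is lost. The size can be stated only as schedule coverage (4 of 6, or 6 of 6, Day 22 counts over six cycles), not as a number of patients or events.

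**What to change.** In the Protocol:

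- Add to Section 5.4.3.6, and to the additional-cycles column of Appendices A and B: *CBC on Day 22 (within 48 hours) of every cycle in which TMZ is given, all patients.*
- In Section 5.4.3.5, let the Phase Ib restriction apply to biochemistry and urinalysis only, so that the blood count covers both phases.
- Bring Section 10.6 and footnote 2 of both appendices into line with this.

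If the sponsor does not want the count after Cycle 2, Section 7.2.2 should say so and name the count that then drives Table 3.

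The cost is one blood draw per TMZ cycle beyond the visit list: n - 2 per patient over n cycles under footnote 2, or n for a Phase II patient under Section 5.4.3.5. No draw is added beyond what Section 7.2.2 already asks for. The SAP needs no change.
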